7. INFORMED CONSENT

Patients enrolled in the study will be given a complete and exhaustive explanation about the nature, purposes, possible risks, and benefits of the study. The patient will be informed that he/she will be free to stop the study at any time. The patient will be given the opportunity to ask questions and will be given as much time as desired to evaluate the information provided. For the pediatric population, consent will be requested from parents in the same way.

The investigating doctor will keep the original of the signed written informed consent.

In the written informed consent form it will be specified that the study data will be stored in computerized form and that the confidentiality of the data itself will be maintained in accordance with the provisions of current legislation.

8. STATISTICAL ANALYSIS

All enrolled patients registered in the registry will be included in the analyses. A descriptive analysis will be performed on the collected data. In general, qualitative variables will be described using frequency distributions; the quantitative variables will be described by mean and standard deviation if normally distributed, and by median and interquartile range if asymmetrically distributed. As appropriate, statistical tests will be used for exploratory purposes. Treatment effects (Change in BPI-S and BPI-I scores) will be calculated as the ratio of the difference between baseline and follow-up scores to the baseline score. If the data allow it, inferential analysis will be applied on quantitative data (such as: comparison of Student's t means, Fisher's F, etc.), or on qualitative data (such as: chi square, odds ratio, Mann Whitney U, etc.). The prevalence of the different pathologies and the related confidence intervals will be estimated. Detailed statistical analysis plans will be set up in future research protocols that will use this database as a source of data.

Sample Size

Since this is an observational registry, no prior sample size calculation is required. Considering an expected participation of 12 centers, an estimate of 2500 patients included appears reasonable.

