- continuously and systematically collect, evaluate, and archive relevant demographic and clinical information on patients belonging to chronic pain treatment centers, making it available for studies and research.
- promote the use of uniform and comparable classification systems, definitions, and records in the structures participating in the database.

- Define the flow of patients referring to pain therapy centers to allow adequate health planning and the priority areas of intervention of the national health plan.

The data collected will facilitate the planning of future studies aimed to:

- define the impact of chronic pain at a local and national level, and its territorial and temporal variations over time, through prevalence and incidence measures;
- identify clinical subtypes, risk factors, predisposing and triggering factors;
- increase knowledge in the field of chronic pain to standardize diagnostic/therapeutic pathways and promote adequate management strategies.

2. Objectives

Primary Outcomes

Identify the profiles of patients belonging to pain therapy centers in terms of:

1. Location and type of pain
2. Prescribed therapies
3. Effectiveness of therapies
4. Time needed to reach the efficacy outcome

Secondary Outcome

1. Evaluate the proportion of patients who reach the outcome of 30 or 50% improvement
2. Evaluate the healthcare resources used in terms of number of visits and time needed to achieve the best outcome (30 or 50% improvement)
3. Identify patient profiles that are related to clinically significant outcomes and the specific treatments performed, plus their intermediate surrogate outcomes in relation to specific patterns

4. Describe the relevant clinical variables in the study population. In particular, the absolute and relative frequencies of those clinical variables relevant to the effectiveness of the treatment will be described, categorized by type of treatment, and the timing of the start of treatment with respect to the onset of pain. The data collected may be used for predictive analyses.

3. Study Design

This is a prospective, multicenter, non-profit observational cohort study. No intervention on patients outside of common clinical practice is envisaged.

The study is divided into three phases.

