5. PROCEDURES EXPECTED AND INFORMATION COLLECTED

Enrollment procedure

Adult patients of both sexes who belong to pain therapy centers with a diagnosis of Chronic Pain (pain that lasts > 12 weeks), regardless of the etiology, modality and age of onset, will be considered eligible for enrollment.

It will be possible to enroll patients during their first visit (FIRST ANESTHESIOLOGICAL VISIT), or during a check-up visit (ANESTHESIOLOGICAL CHECK-UP VISIT) or during a scheduled hospitalization for pain procedures (ORDINARY OR DAY HOSPITAL ADMISSION)

Patients will be asked to join the study after having been informed in detail (also with the aid of a written information form) of the objectives of the project, as well as the methods with which these objectives will be pursued. Participants will be informed about the lack of informative feedback regarding the results of future clinical evaluations: the results of any research originating from the register, in fact, will not be delivered to the participants themselves. The subject who freely accepts will authorize the inclusion of their data in the project by signing the informed consent form of which they will receive a copy. It will also be clearly explained in the information sheet attached to the informed consent that each participant will have the possibility of withdrawing their participation from the study at any time, without providing any reason and without this jeopardizing the doctor-patient relationship with the specialists involved in the project.

Patients will be informed by the manager of the patient's pain center or the principal investigator for the center (assuming this is not the same individual).

The doctor will complete the electronic CRF after evaluating the patient and classifying him according to the criteria of the IASP (International Association for the Study of Pain) in terms of primary or secondary chronic pain. In the case of a patient enrolled during a check-up or during hospitalization, all data relating to the time in which the patient is in care at the center, the

invasive procedures previously undertaken, the drugs prescribed, will be collected. Retrospective data (only for patients already being treated at the center) will be collected according to a predefined group (e.g.: the patient has been in the care of the center for: > 5 years; from 1 to 5 years; from 1 year to 6 months; from 3 to 6 months; < 3 months).

[figure not shown]
Follow-up procedure

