6. ENDPOINT

Primary Endpoint

The number of patients referring to the centers, the type of pain, the proportion of patients who reach the clinically significant outcome, the type of therapies prescribed (pharmacological, neuromodulatory or implanted) necessary to achieve the outcome and the number of accesses and the Time in which a clinically significant improvement will be achieved (Change in BPI-s or BPI-I; a reduction of > 30% is considered clinically significant and a reduction of > 50% is considered optimal, the data will be evaluated for each Item).

Secondary Endpoint

1. The effectiveness of the treatments will be described in terms of
 - a. Change in pain intensity according to the Brief Pain Inventory-Severity questionnaire (BPI-S) A reduction of > 30% is considered clinically significant and optimal a reduction > of 50% the data will be evaluated for each Item)
 - b. b. Change in pain interference on daily activities according to the Brief Pain Inventory-Interference questionnaire (BPI-I). A reduction of > 30% is considered clinically significant and a reduction of > 50% is considered optimal; the data will be evaluated for each item)
2. Proportion of patients achieving clinically significant outcomes in relation to baseline characteristics and specific treatments performed and their intermediate surrogate outcomes in relation to specific patterns.
3. Resources used: Number of visits to the center for each patient in a year; Number of ordinary or day hospitalizations for each patient in a year.
4. The clinical variables relevant to the outcome will be described (e.g. type of pain, comorbidities, the time between treatment and clinically significant improvement, type of therapy undertaken - pharmacological, invasive, implant-based)

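### Section 8's default of median and IQR for skewed variables suits the yearly hospitalisation count poorly; add the total, the share admitted and the mean rate

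*Protocol*

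**What the plan says.** Protocol Section 8 (Statistical Analysis) gives one rule for describing data. It opens "In general, qualitative variables will be described using frequency distributions" and continues that "the quantitative variables will be described by mean and standard deviation if normally distributed, and by median and interquartile range if asymmetrically distributed". No separate summary is named for counts, and none is excluded.

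Protocol Section 6, Secondary Endpoint 3 (resources used), has two parts: "Number of visits to the center for each patient in a year" and "Number of ordinary or day hospitalizations for each patient in a year".

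Two statements of purpose bear on how these counts will be used. Section 1, under the purposes of the database, includes "Define the flow of patients referring to pain therapy centers to allow adequate health planning". Section 2, second secondary outcome, is worded "Evaluate the healthcare resources used in terms of number of visits and time needed to achieve the best outcome"; it does not name hospitalisations.

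No expected admission rate is stated anywhere. Section 5 allows patients to be enrolled at a first visit, at a check-up, or during an ordinary or day-hospital admission.

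**The concern.** A yearly admission count cannot fall below zero, and it is typically zero for many patients and high for a few. Such a variable is asymmetric, so the Section 8 default points to median and IQR. Those statistics describe the middle half of patients. When most patients have no admission, the middle half holds no information on how many admissions there were.

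At stake is whether the reported figure for the hospitalisation part of the endpoint tells the reader anything about volume. Resource planning works with totals and mean rates, and neither can be recovered from a published median and IQR. Two centres or therapy groups with very different admission volumes could show identical summaries.

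**Working it through.** **Inputs**

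- Number of patients: N = 2500, from Section 8, Sample Size ("Considering an expected participation of 12 centers, an estimate of 2500 patients included appears reasonable"). This is a feasibility estimate, used here only to turn rates into totals.
- Share of patients admitted in a year: not in the documents. Assumed, from 2% to 52%.
- Number of admissions among those admitted: not in the documents. Assumed as stated below.

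The plan has no figure of its own on this point to reproduce.

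**Step 1. When is the summary 0 (0–0)?** Let k be the number of patients with at least one admission. In sorted order the first N − k values are 0. The upper quartile is 0 when k/N < 0.25, that is, k < 2500 × 0.25 = 625. Checked numerically under five quartile definitions:

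- k = 624 (24.96%): 0 (0–0) under all five.
- k = 625 (25%): the upper quartile lies between 0 and 0.75, depending on the definition.
- k = 626 (25.04%): 0 (0–1) under all five, where most admitted patients have one admission.
- The median leaves 0 only at about 50% admitted; at 52% it is 1.

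**Step 2. What does the summary hide?** Total = N × share admitted × admissions per admitted patient. The mixed rows assume that, of those admitted, 70% have one admission, 20% two and 10% four: 0.7 × 1 + 0.2 × 2 + 0.1 × 4 = 1.5 per admitted patient.

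| Assumption | Total admissions | Per 100 patients | Default summary |
|---|---|---|---|
| 2% admitted once | 2500 × 0.02 × 1 = 50 | 2 | 0 (0–0) |
| 24% admitted once | 2500 × 0.24 × 1 = 600 | 24 | 0 (0–0) |
| 24% admitted three times | 2500 × 0.24 × 3 = 1800 | 72 | 0 (0–0) |
| 10% admitted, mixed | 250 × 1.5 = 375 | 15 | 0 (0–0) |
| 20% admitted, mixed | 500 × 1.5 = 750 | 30 | 0 (0–0) |
| 30% admitted, mixed | 750 × 1.5 = 1125 | 45 | 0 (0–1) |
| 40% admitted, mixed | 1000 × 1.5 = 1500 | 60 | 0 (0–1) |

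The first and third rows differ by a factor of 1800/50 = 36 and read the same. The last two rows show that passing 25% helps only a little.

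**Step 3. What mean rate does the 25% threshold correspond to?**

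- Poisson: 1 − exp(−λ) = 0.25 gives λ = −ln 0.75 ≈ 0.288 admissions per patient-year.
- Negative binomial with mean m and size r: P(at least one) = 1 − (r/(r + m))^r. For m = 0.3 this is 1 − 1/1.3 = 23.1% at r = 1, and 1 − 0.5^0.3 = 18.8% at r = 0.3.
- A Poisson mean of 0.3 gives 1 − exp(−0.3) = 25.9%.

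So the same mean of 0.3 (2500 × 0.3 = 750 admissions) reads 0 (0–0) or 0 (0–1) depending only on how clustered the admissions are. Negative binomial means of 0.5 and 0.8 (1250 and 2000 admissions) both read 0 (0–1) for r from 0.3 to 1.

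**Step 4. Visits.** Every patient enters at a visit or admission, so take a count that starts at 1: 1 plus a negative binomial with mean 3 and r = 1 or 2 (assumed). The mean is 4 and the median is 3 in both cases. The median is a fair description of the typical patient. The workload is 2500 × 4 = 10,000 visits, while 2500 × 3 = 7,500. The median therefore does not give workload, though it does not collapse to zero either.

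**The case against.** There is a good deal to say for the plan.

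- **The rule is a default.** The sentence opens in general terms and bars no added total, mean or share. A reader might infer that every skewed variable must be shown by median and IQR alone; the text does not say so. This stands. What remains is that no other summary is named for a count.
- **The condition may not apply.** No admission rate is given, day hospitalisations count, and enrolment can take place during an admission, so a share above 25% cannot be ruled out. This also stands, and the 0 (0–0) result is therefore conditional. Steps 2 and 3 show, however, that the summary stays coarse somewhat above 25%.
- **Resource use does not vanish.** A reader might infer that the whole endpoint is lost. Visits form its other part and would not be reported as zero; the Section 2 objective is worded in visits and time; and the primary endpoint includes the number of patients referred and the number of accesses.
- **Visit workload is not understated by the plan.** A reader might infer a 25% shortfall from multiplying the median by 2500. The protocol proposes no such multiplication. Attachment 1 requires a form at each visit or admission, so totals can simply be counted.
- **This may be detail for an SAP.** Display of one secondary count is often settled there, and an SAP may exist. But Section 8 does state a summary rule, and it assigns detailed analysis plans to later protocols that will use the database, not to this study's own report. Improving the stated rule is a fair request, though a small one.

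**Conclusion.** The point holds as a minor one. Median and IQR, used as the only summary, are a poor choice for yearly hospitalisations. Below 25% of patients admitted, the result is 0 (0–0) regardless of volume, so 50 and 1800 admissions in 2500 patients cannot be told apart. Somewhat above 25%, totals such as 1125 and 1500 still share the summary 0 (0–1). The threshold is arithmetic. Whether this registry falls below it, and the admission patterns used above, are assumptions, because the documents give no rate.

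For visits, the default gives a usable picture of the typical patient and lacks only the workload figure. A reader might conclude that the registry cannot answer its planning question. The documents do not support that: the patient-level counts are kept, so any loss is in the reported summary and can be reversed.

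**What to change.** Add one sentence to Section 8, for example: *For Secondary Endpoint 3, whatever the skewness, hospitalisations will be reported as the total number, the share of patients with at least one, and the mean rate per patient-year with a robust or bootstrap 95% confidence interval; visits will also be given as a total and a mean rate per patient-year; median and interquartile range will be kept as an additional description.*

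The cost is that sentence and a few lines of analysis. No new data are needed, because the form is already completed at every visit or admission.

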1. RATIONALE TO SUPPORT THE ESTABLISHMENT OF THE DATABASE

The IASP (International Association for the Study of Pain) defines pain as an unpleasant sensory and emotional experience associated with actual or potential tissue damage or described in terms of such damage¹. The physiological function of pain is to serve as a warning sign of a medical condition or injury. In these cases, treatment of the underlying medical condition is critical and can resolve the pain. However, pain may persist despite adequate management of the underlying condition, or the underlying medical condition may not be successfully treated. If the pain persists or recurs for more than three months, the pain is defined as chronic^{2,3}. Long considered a non-life-threatening condition and often overlooked, persistent pain over time can actually become the sole or predominant clinical problem in some patients, generating a chronic condition that significantly impacts patients' quality of life through a wide range of negative physical, psychological and functional effects that limit social participation^{4,5,6}. For this reason, chronic pain is a condition that deserves a specific diagnostic evaluation and appropriate therapeutic efforts, integrated in a multidisciplinary context of physical and psychological rehabilitation. According to many authors, access to adequate pain care should be considered a human right^{7,8}. Recent observations have highlighted a worrying prevalence of pain throughout the world, with significant variations between countries (ranging from 9, 9% to 50.3%)⁹. For this reason, and due to the impact that chronic pain has on healthcare spending, adequate pain control is considered a global health priority. In fact, chronic pain causes the greatest loss of productivity compared to any other health condition¹⁰ and constitutes a significant share of healthcare spending with costs reaching 3-10% of the gross domestic product of European countries^{11,12}.

An important milestone in the European health regulatory framework is represented by Law 38/2010, which established the citizen's right to not suffer¹³. The law paved the way for recommendations to develop structures dedicated to palliative care and pain therapies and to organize hospital and outpatient facilities to guarantee diagnostic-therapeutic continuity for patients with chronic pain. Nonetheless, the provision of adequate care appears difficult to apply

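### Uncontrolled change from baseline is labelled treatment effect and effectiveness of therapies, although it also contains natural fluctuation of pain and possibly regression to the mean

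*Protocol*

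**What the plan says.** Section 8 (Statistical Analysis) defines the outcome quantity: "Treatment effects (Change in BPI-S and BPI-I scores) will be calculated as the ratio". The numerator is baseline minus follow-up and the denominator is baseline. No comparator enters the formula.

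The label carries into the aims. Section 2 (Primary Outcomes) lists "Effectiveness of therapies" as item 3 and the time to reach efficacy as item 4. Section 6 (Secondary Endpoint, item 1) says "The effectiveness of the treatments will be described in terms of" change in BPI-S and BPI-I. It applies two limits: "a reduction of > 30% is considered clinically significant and a reduction of > 50% is considered optimal". The primary endpoint in Section 6 also presents the prescribed therapies as what was needed to reach the outcome.

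On design, Section 3 says "This is a prospective, multicenter, non-profit observational cohort study". Section 4 admits patients with NRS > 4 but gives no item, recall period or date for that score. Section 5 (Enrollment procedure) says "It will be possible to enroll patients during their first visit", or at a check-up visit or scheduled admission. Attachment 1 allows for patients who have been in care for more than 5 years. It records three severity items over the last 24 hours and a fourth for current pain, and it has no separate NRS field. Section 1 acknowledges a recurrent course: "If the pain persists or recurs for more than three months, the pain is defined as chronic".

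**The concern.** A fall in pain between two clinic contacts has several sources: the therapy, day-to-day and week-to-week variation, the natural course of the condition and, where entry depends on a high score, regression to the mean. The formula in Section 8 adds these together and names the sum after one of them. With a 24-hour or current-pain recall, short-term variation goes straight into both scores.

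For patients enrolled at a check-up or admission the label is weaker still, because their baseline may already be under treatment.

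At stake is how the registry's main results are read. Response proportions and changes, overall and by therapy, would be reported as effectiveness when a therapy with no effect would also produce some responders.

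**Working it through.** **The plan's own figures.** There is no assumed change, SD or response rate to reproduce. The 2500 patients from 12 centres in Section 8 are a feasibility estimate.

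**Question.** What would the formula return if therapy did nothing?

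**Inputs from the Protocol.** Entry score > 4 (5 or more in whole numbers, so a cut at 4.5); severity items scored 1 to 10 (Attachment 1); response = (baseline − follow-up) / baseline > 0.30 (Sections 6 and 8).

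**Assumptions, not in the Protocol.** Each patient has a constant level, drawn from a normal distribution with mean μ of 5, 6 or 7 and SD 2. Each visit adds independent normal variation with SD s of 1.0, 1.5 or 2.0. Scores are rounded and limited to 1–10. In the first case the qualifying score is also the baseline.

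**Closed form for the mean fall.** Expected fall = SD × (1 − ρ) × φ(a) / (1 − Φ(a)), with a = (4.5 − μ) / SD. For μ = 5 and s = 1.5:

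- SD = √(2² + 1.5²) = 2.5 and ρ = 4 / 6.25 = 0.64
- a = (4.5 − 5) / 2.5 = −0.20, and φ(a) / (1 − Φ(a)) = 0.391 / 0.579 = 0.675
- expected fall = 2.5 × 0.36 × 0.675 = 0.61 points
- mean baseline = 5 + 2.5 × 0.675 = 6.69, so the fall is 0.61 / 6.69 = 9% of it

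**Simulation, 400,000 patients per setting, no treatment effect, one later visit.** The last column keeps the entry threshold but takes baseline from a separate measurement.

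| μ | s | Mean fall, qualifier = baseline | > 30% fall, qualifier = baseline | > 30% fall, no threshold | > 30% fall, separate baseline |
|---|---|---|---|---|---|
| 5 | 1.0 | 0.32 | 11.9% | 13.1% | 7.8% |
| 5 | 1.5 | 0.62 | 23.0% | 20.4% | 16.0% |
| 5 | 2.0 | 0.96 | 31.4% | 25.2% | 22.0% |
| 6 | 1.0 | 0.21 | 8.3% | 9.2% | 5.9% |
| 6 | 1.5 | 0.42 | 17.5% | 16.4% | 13.2% |
| 6 | 2.0 | 0.69 | 24.8% | 21.5% | 18.7% |
| 7 | 1.0 | 0.12 | 5.5% | 6.0% | 4.3% |
| 7 | 1.5 | 0.27 | 12.6% | 12.2% | 10.3% |
| 7 | 2.0 | 0.47 | 18.9% | 17.4% | 15.3% |

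With a separate baseline the mean fall is 0.00 in every row.

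**Other assumptions.** With total SD 2, between-visit correlation 0.5 to 0.85 and population mean 4 to 7, the mean fall is 0.06 to 0.96 points and 2.7% to 33.0% exceed 30% at one visit. With a separate baseline, 2.0% to 19.7% do. The order of size is the same.

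**Reading the table.** Only the mean fall isolates selection by the threshold. The response proportions come mostly from ordinary two-way fluctuation: at s = 1.5, 23.0% with the threshold against 20.4% without it (μ = 5), and 17.5% against 16.4% (μ = 6). Part of the no-threshold figure comes from low baselines, where a small drop already exceeds 30%.

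**The case against.** The strongest defence is that the Protocol calls the analysis descriptive, uses tests for exploratory purposes, says openly that the study is observational and leaves detailed analysis plans to later protocols. An untreated comparator is not available in a registry of routine care. All of this is true, and no comparator is asked for. It does not cure the label, because this Protocol itself fixes the definition, names it treatment effect and makes effectiveness a primary outcome.

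Four stronger readings are tempting, and the documents do not support them.

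- *That the NRS > 4 criterion produces most of the apparent responders.* It does not; the table shows that fluctuation does. Regression from the cut also needs the qualifying score to be, or be closely tied to, the BPI baseline, which the Protocol does not say.
- *That unlimited follow-up means any visit above 30% counts as response.* The Protocol states no best-of-several-visits rule, so no figure should rest on one.
- *That every therapy would look effective.* The mean fall without any effect is at most about 1 point in these settings and 9% of baseline in the worked case, well below the 30% limit. It is a tendency.
- *That these results would directly set therapeutic pathways.* Section 1 says that the data help to plan future studies with that aim.

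**Conclusion.** The label is wrong as written. An uncontrolled within-patient change cannot be called the effect of treatment or the effectiveness of a therapy, and the Protocol does so in Sections 2, 6 and 8.

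The size cannot be fixed from the documents. Under the stated assumptions, a therapy with no effect gives about 6% to 31% responders above 30% at one visit and a mean fall of about 0.1 to 1.0 points when the qualifier is also the baseline. With a separate baseline it gives about 4% to 22% responders and a mean fall of about zero. If most patients sit well above 4, the threshold adds little. It should also act less directly on BPI-I, since entry depends on pain intensity. The objection to the label holds in all these cases, because fluctuation remains.

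**What to change.** 1. In Sections 2, 6 and 8, replace treatment effects and effectiveness of therapies or treatments with change from baseline under the centre's care. In the primary endpoint of Section 6, refer to therapies received and not to therapies needed to reach the outcome.
2. State that the change and the > 30% and > 50% proportions, overall and by therapy, include fluctuation and regression to the mean and do not estimate the effect of any therapy.
3. Report the proportion worsening by > 30% next to the proportion improving by > 30%. This gives context and is not a test: with no effect the two need not match. At μ = 5 and s = 1.5 the simulation gives 23.0% improving and 11.2% worsening when the qualifier is the baseline, and 16.0% and 23.1% with a separate baseline.
4. Report patients enrolled at a first visit separately from those already in care. Attachment 1 records which they are.

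Two other remedies are not advised. Making one BPI item both the entry qualifier and the response item would create the very condition that maximises regression to the mean. A benchmark from intervals with unchanged therapy is not reliable, because Attachment 1 has no dose field and dose changes would be invisible.

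The cost is wording plus two descriptive tabulations on data already planned. The downside is a less favourable claim.
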